8.1 Primary Outcome and Analyses

The primary outcome of each participant is the area under the stimulated C-peptide curve (Y_{AUC}) over the first 2 hours of a mixed meal glucose tolerance test conducted at the one-year visit. The Y_{AUC} is computed using the trapezoidal rule which translates into a weighted sum of the timed C-peptide values over the 120 minute MMTT. The more appealing quantity is the AUC mean which is $\frac{Y_{AUC}}{120}$ in nmol/L and will be denoted as Y_{Cp} .

Let $Y_{Cp}^{ATG/GCSF}$, Y_{Cp}^{ATG} , and $Y_{Cp}^{Control}$ represent the C-peptide AUC mean for study patients receiving both ATG and GCSF, receiving ATG alone, and those receiving placebo, respectively. Likewise, let $\mu_{Cp}^{ATG/GCSF}$, μ_{Cp}^{ATG} , and $\mu_{Cp}^{Control}$ represent the population mean of C-Peptide for these groups at one year, respectively.

The primary statistical hypotheses to be assessed in the study are:

$$H_0: \mu_{Cp}^{ATG/GCSF} = \mu_{Cp}^{Control} \text{ versus } H_a: \mu_{Cp}^{ATG/GCSF} > \mu_{Cp}^{Control}$$

$$H_0: \mu_{Cp}^{ATG} = \mu_{Cp}^{Control} \text{ versus } H_a: \mu_{Cp}^{ATG} > \mu_{Cp}^{Control}$$

The primary analysis will be conducted on a transformed scale using the function $\log(Y_{Cp} + 1)$. This provides better normal distributional behavior by the test statistic. The comparison between any two treatment arms will be based on a Wald test of treatment effect in an ANCOVA model adjusting for gender, baseline age, and baseline $\log(Y_{Cp} + 1)$.

8.2 Secondary Outcome and Analyses

Additional analyses of the primary outcome to determine the effect of ATG with and without GCSF include:

- C-peptide AUC mean at 3, 6, 9, 12, 18, and 24 months using the ANCOVA mentioned above.
- The hazard rate of C-peptide failure (C-peptide failure defined as the first occurrence at which the 2 hour peak C-peptide < 0.2 nmol/L during a MMTT) using the proportional hazards model⁸² while adjusting for baseline level of C-peptide, gender and baseline age.
- Longitudinal analyses of C-Peptide AUC means 3, 6, 9, 12, 18, and 24 months using a mixed effects model⁷² with a random intercept and slope by subject, adjusted for the baseline level of C-peptide, gender and baseline age. The mean intercept and slope will be compared between treatment groups.
- Treatment interactions with the covariates baseline C-peptide, gender and baseline age will be analyzed with a homogeneity test categorizing the continuous variables into 3 approximately equal groups; ladder plots will be constructed. Other variables to be tested for treatment interactions are HbA1c levels, HLA, other genotype and immune phenotypes, and race/ethnicity, as appropriate.

Additional secondary objectives to determine the effect ATG with and without GCSF has on the following:

- HbA1c, Insulin dose (units/kg) and Blood glucose over time by treatment group using ANCOVA.
- Adverse events
 - Number and severity.
 - The rates of severe adverse events will be computed (total number of events divided by total subject years of follow-up).
- Hypoglycemia
 - Number of major hypoglycemic events (defined as loss of consciousness, seizure, or requiring assistance from another person because of altered state of consciousness).
 - Reported hypoglycemic events confirmed with capillary blood glucose measurement less than 70 mg/dl.
 - The rates of severe hypoglycemic will be computed (total number of events divided by total subject years of follow-up).
- For individuals with continuous glucose monitoring data available

- Area under the curve and number of events less than 70 mg/dl on the continuous glucose monitoring record.
- Hyperglycemia measured as the area under the curve and number of events greater than 180 mg/dl on the CGMS record prior to each study visit.
- Glycemia and glycemic variability prior to each MMTT visit
- The daily mean level of glucose, as well as the levels before and after meals will be computed.
- Measures of diurnal variability in glucose will be measured by the J-value, standard deviation of glucose values, and the mean amplitude of glycemic excursion (MAGE).

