8.4 Sample Size and Power Calculations

The primary analysis will compare the difference in C-Peptide between experimental and placebo treatment groups at 12 months using $\log(Y_{Cp} + 1)$ transformation and ANCOVA model adjusting for gender, baseline age and the baseline value of $\log(Y_{Cp} + 1)$. Estimates of the mean and standard deviation of $\log(Y_{Cp} + 1)$ (expressed algebraically as: $\hat{\mu}_{\log(Y_{Cp} + 1)}$ and $\hat{\sigma}_{\log(Y_{Cp} + 1)}$) in the placebo group were derived from the last four TrialNet studies of early onset disease. The 90% confidence bound estimates were used to provide good confidence that this trial's study population characteristics fall within these limits to assure the advertised statistical power; the estimates are $\hat{\mu}_{\log(Y_{Cp} + 1)} = 0.360$ and $\hat{\sigma}_{\log(Y_{Cp} + 1)|X} = 0.167$ (i.e., the residual mean squared error regressing on gender, baseline age and C-peptide). The geometric-like mean of Y_{Cp} for the placebo group is $\exp(0.36) - 1 = 0.433$ nmol/L.

Using standard equations for the comparison of two means and a 1:1:1 allocation, a sample size of 78 participants (26 per group) with complete data would provide power of 85% to detect a 50% increase in the geometric-like mean in either experimental treatment group (compared to the control) using the Wald test (from the adjusted linear model) at the 0.025 level (one-sided). Thus the overall Type I error for both tests is approximately 0.05.

Assuming that 10% of the participants will have missing data (one-year MMTT was not done or subject withdrew prior to the one-year assessment), the sample size goal for this study will be set at 84 participants (28 per group).

The study will be closed to additional participants when the total number then randomized plus a fraction of those in screening (i.e., screening for eligibility) is expected to provide the proper number of eligible participants. Participants who had already conducted the initial screening visit at that time will be allowed to complete screening and be randomized if both consenting and eligible.

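### Section 8.2 tests interactions with baseline age and baseline C-peptide only after cutting each into thirds, which costs power if the effect changes roughly linearly with them

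*Protocol*

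**What the plan says.** Among the further analyses of the primary outcome, Protocol section 8.2 has an item that opens "Treatment interactions with the covariates baseline C-peptide, gender and baseline age" and says that these "will be analyzed with a homogeneity test categorizing the continuous variables into 3 approximately equal groups". Ladder plots are announced in the same sentence as a separate product, so the thirds define the test and not only the display. The protocol mentions no interaction term with a continuous covariate.

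Section 8.1 bases the primary comparison on "a Wald test of treatment effect in an ANCOVA model adjusting for gender, baseline age, and baseline" log(Y_Cp + 1), with no categorisation stated. Section 8.4 takes its residual SD of 0.167 from a model on the same covariates, described as "the residual mean squared error regressing on gender, baseline age and C-peptide".

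Sections 8.2 and 8.4 give no power, significance level or effect size for any interaction test.

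**The concern.** Baseline age and baseline C-peptide enter the primary model without being cut, but are cut into thirds for the analysis that asks how the treatment effect varies along them. Everyone within a third is then treated as alike, and one slope difference per contrast becomes two free differences. No reason is given.

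At stake is a secondary reading of the trial: whether benefit rises or falls with age (eligibility runs from 12 to under 46 years, section 3.1.1) or with residual beta-cell function. With 26 completers per arm, each third holds about 26/3 = 8.7 people per arm, so there is little information to give away.

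**Working it through.** **Inputs from the Protocol.** Control mean 0.360 on the log(Y+1) scale; residual SD 0.167; 50% increase in the geometric-like mean; 26 per group; one-sided 0.025; power 85% (all section 8.4).

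**Assumptions, not in the Protocol.** Interaction tests at two-sided 0.05; a linear interaction; an unordered homogeneity test; a benchmark power of 80% for the continuous test.

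**1. Reproduce the plan's own figure.**
- Design effect: ln(1 + 1.5 × (exp(0.36) − 1)) − 0.36 = ln(1.65) − 0.36 = 0.1408.
- n per group: 2 × (1.960 + 1.036)² × 0.167² / 0.1408² = 25.3, rounded up to 26. Power at 26 is 86%. The stated size reproduces, so the scale used below is the plan's own.

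**2. Information kept by thirds.** This is the between-thirds variance divided by the total variance.
- Normal covariate: 6 × φ(0.4307)² = 0.793, so 20.7% is lost.
- Uniform on 12 to 46: 0.889 (11% lost).
- Moderately right-skewed: 0.716 (lognormal, log-SD 0.4) and 0.732 (truncated exponential on 12 to 46), so 27% to 28% lost.
- Strongly skewed (lognormal, log-SD 0.6): 0.627 (37% lost).

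**3. Power for a linear interaction, one active arm against placebo.** 80% power on 1 df needs a noncentrality of 7.85. Multiply it by the share kept and test on 2 df.
- Normal: 0.793 × 7.85 = 6.23, power 60%. The information loss alone, still on 1 df, gives 70%; the extra degree of freedom accounts for the rest.
- Uniform 65%; moderately skewed 55% to 56%; strongly skewed 50%.

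**4. Three arms jointly.** 80% power on 2 df needs 9.63. On 4 df after cutting, power is 58% for a normal covariate, with a range of 47% to 64% by shape.

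**5. Small-sample checks, normal covariate.**
- F tests: 80% becomes 58.9% at n = 52 and 56.9% at n = 78.
- Simulation at n = 52 (4,000 runs, slope difference 0.135 per SD): 77% continuous against 53% for thirds. With no interaction, both reject in about 5% of runs.

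**6. What the trial can detect either way.**
- For n = 52, the slope difference per covariate SD that gives the continuous test 80% power is √7.85 × 2 × 0.167 / √52 = 0.130, or 0.130/0.1408 = 92% of the design effect.
- At half the design effect per SD, the noncentrality is 0.0704² × 52 / (4 × 0.167²) = 2.31. Power is 33% continuous against 21% for thirds. Simulation with F tests gave 30% against 18%.

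**7. Other shapes (simulation, n = 52).**
- Step at the upper third: 50% continuous against 54% for thirds.
- U-shape: 14% against 16%.

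**The case against.** The strongest case for the plan is that the shape of any interaction is unknown. Thirds impose no straight line, and the advantage of the product term depends on one. A monotone step is enough to remove it, as step 7 shows; a non-monotone pattern is not required. With 52 people per contrast, a product term can also be driven by a few extreme baseline values. These points stand, and they are the cost of the change.

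A reader might infer that the trial's interaction test drops from 80% to 60% power. The documents do not support that. The protocol assigns interactions no power, and a continuous test would reach 80% only for a gradient almost as large as the whole design effect per SD. For gradients half that size, both tests would usually miss.

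A reader might also take age and residual function to be the central effect-modification question. Section 8.2 lists them with gender, then HbA1c, HLA, other genotypes, immune phenotypes and race/ethnicity, and ranks none first. Nor is there room for choosing cut points to suit the result: equal-sized thirds are a prespecified rule that does not use outcomes.

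Finally, a separate statistical analysis plan could add a continuous interaction without contradicting section 8.2. That helps only in part, because the protocol does name the categorised test.

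**Conclusion.** The point holds as a minor one. Section 8.2 fixes a test that is less efficient for a gradient. For a roughly linear interaction in a normal covariate it gives up about 21% of the information and doubles the degrees of freedom, taking a benchmark 80% to about 60% (50% to 65% across the covariate shapes examined; 58% for three arms with a normal covariate). These figures rest on linearity, an unordered homogeneity test and two-sided 0.05. At half the design effect per SD the gain from staying continuous is about 12 points, on a test that is weak either way.

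It would be wrong to read this as a flaw in the main result. By the text of sections 8.1 and 8.4 to 8.7, no interaction result enters the primary tests, the choice between active arms, the sample size re-estimation or the stopping rules.

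**What to change.** In section 8.2, state that treatment-by-age and treatment-by-baseline log(Y_Cp + 1) interactions are tested as product terms with the continuous covariates in the ANCOVA of section 8.1. Keep the thirds and the ladder plots as descriptive displays, where a step or a bend would still show. Gender stays categorical.

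The cost is one sentence and no new data. The statistical price is no advantage, or a few points less power, for step and non-monotone patterns, plus some sensitivity to extreme baseline values.

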8.3 Additional Outcomes and Analyses

Additional outcomes of interest include the effects of ATG with and without GCSF treatment with regard to the Mechanistic Studies assessed from blood draws as outlined in the Schedule of Assessments. These measures include, but are not limited to, exploration of pharmaco-genetic signatures that may differentiate response to treatment, and the relationship between hsCRP and IL-1 β levels and beta cell function and/or other metabolic measures.

Additional analyses will compare the results in this trial to other trials using ATG and GCSF and other TrialNet studies. Data in this trial will be used in conjunction with other TrialNet data for exploratory analysis.

8.4 Sample Size and Power Calculations

The primary analysis will compare the difference in C-Peptide between experimental and placebo treatment groups at 12 months using $\log(Y_{Cp} + 1)$ transformation and ANCOVA model adjusting for gender, baseline age and the baseline value of $\log(Y_{Cp} + 1)$. Estimates of the mean and standard deviation of $\log(Y_{Cp} + 1)$ (expressed algebraically as: $\hat{\mu}_{\log(Y_{Cp} + 1)}$ and $\hat{\sigma}_{\log(Y_{Cp} + 1)}$) in the placebo group were derived from the last four TrialNet studies of early onset disease. The 90% confidence bound estimates were used to provide good confidence that this trial's study population characteristics fall within these limits to assure the advertised statistical power; the estimates are $\hat{\mu}_{\log(Y_{Cp} + 1)} = 0.360$ and $\hat{\sigma}_{\log(Y_{Cp} + 1)|X} = 0.167$ (i.e., the residual mean squared error regressing on gender, baseline age and C-peptide). The geometric-like mean of Y_{Cp} for the placebo group is $\exp(0.36) - 1 = 0.433$ nmol/L.

Using standard equations for the comparison of two means and a 1:1:1 allocation, a sample size of 78 participants (26 per group) with complete data would provide power of 85% to detect a 50% increase in the geometric-like mean in either experimental treatment group (compared to the control) using the Wald test (from the adjusted linear model) at the 0.025 level (one-sided). Thus the overall Type I error for both tests is approximately 0.05.

Assuming that 10% of the participants will have missing data (one-year MMTT was not done or subject withdrew prior to the one-year assessment), the sample size goal for this study will be set at 84 participants (28 per group).

The study will be closed to additional participants when the total number then randomized plus a fraction of those in screening (i.e., screening for eligibility) is expected to provide the proper number of eligible participants. Participants who had already conducted the initial screening visit at that time will be allowed to complete screening and be randomized if both consenting and eligible.

In the situation where both hypotheses are rejected in favor of the experimental regimen, then it is appropriate to decide which experimental regimen should be considered first for additional clinical trials. If ATG and ATG+GCSF truly differ in efficacy, it is not expected that the difference would be as large as the effect size used in this design. Thus requiring the difference to reach statistical significance would be too stringent due to the lack of statistical power. The plan is to employ the method of Simon⁸¹ to select the treatment with the largest geometric-like mean in C-Peptide regardless of how small the difference is over the other experimental regimen. Formally, the decision rule is to select the experimental regimen with highest predicted mean based on the fitted linear regression model of C-Peptide used in the formal hypothesis tests. Given the one experimental treatment is associated with 25% higher mean (half of the design effect size) compared to the other experimental treatment, the probability is 96% that the most efficacious regimen will be selected with this decision rule. Even if the increase is only 12.5% (i.e., a fourth of the design effect size), the probability is 82% in making the right choice. Since under the null ($\mu_{Cp}^{ATG} = \mu_{Cp}^{ATG/GCSF}$) we consider selecting either treatment a non-error there is no contribution to the type I error, and therefore, no further adjustment is required to the α -level of the initial two pair-wise tests.

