8.6 Interim Monitoring Plan

Interim analyses will be conducted periodically during the study and will be reviewed by the TrialNet DSMB for assessment of effectiveness and safety. The Lan-DeMets⁷⁴ spending function with an O'Brien-Fleming boundary will be used to protect the type I error probability from early and multiple testing and to assess the significance of the interim results that emerge during the trial⁸². The spending function that approximates the O'Brien-Fleming boundaries is:

$$\alpha_1(t^*) = 2 - 2\Phi\left[\frac{Z_{\alpha/2}}{\sqrt{t^*}}\right]$$

where t^* is the information fraction ($0 < t^* \leq 1$), α_1 is the α -level of the interim (one-sided) test and α is the type I error for one of the pair-wise tests (i.e., 0.025). The monitoring plan will allow for early termination based on the treatment effect on C-peptide values at 1 year of follow-up using the ANCOVA model described above.

The DSMB will also be informed if there is a serious lack of evidence of a treatment effect (i.e. futility analysis). The boundaries are based on the paper by Lachin⁸³. The study arm should be "closed" based on the futility of rejecting the null hypothesis at the completion of the trial if: $z_{ATG}(t^*) \leq 0.1$ when $0.5 \leq t^* < 0.75$ or if $z_{ATG}(t^*) \leq 1.0$ when $t^* \geq 0.75$ (z is the Wald test of the treatment effect coefficient). The same rule would be applied to the ATG/GCSF treatment group. These $t^* = 0.5$ and 0.75 are equivalent to when there are 39 and 59 participants with one-year C-peptide results, respectively. Lachin showed that a onetime use of either boundary for the design parameters above ($\theta \equiv Z_{1-\alpha} + Z_{1-\beta} = 3.00$) raises the type II error to approximately 0.15414 and 0.15611, respectively. For larger values of t^* the increase to the error probability is even less. Furthermore, by the laws of probability a single use of each rule will increase the type II error no more than the sum of the increase (i.e., $0.00414 + 0.00611 = 0.0103$).

[figure not shown]

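### The two fixed one-sided 0.025 tests are valid but do not fully use the stated overall error of about 0.05; a Holm step-down would raise the chance of confirming both arms at little cost

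*Protocol*

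**What the plan says.** Protocol 8.1 sets two primary hypotheses, ATG/GCSF against placebo and ATG against placebo, both one-sided. Section 8.4 tests each at one-sided 0.025 and concludes: "Thus the overall Type I error for both tests is approximately 0.05". Its power figure, for 26 complete participants in each group, is 85% per comparison, and the target is "to detect a 50% increase in the geometric-like mean in either experimental treatment group". Section 8.6 carries the same 0.025 into the Lan-DeMets spending function for each pair-wise test.

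The rule for choosing between the two active regimens, also in 8.4, is introduced with "In the situation where both hypotheses are rejected in favor of the experimental regimen", and the protocol states that this choice calls for no further adjustment of the level. Section 8.7 adds that a crossing of the efficacy boundary would normally close the placebo arm, which removes the second formal test.

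Nowhere does the protocol raise the level of the remaining test after the first null is rejected. It gives power for each comparison but not the probability of rejecting both.

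**The concern.** Two fixed tests at 0.025 are a plain Bonferroni split of 0.05. Once one null has been rejected, only one remains, and the whole 0.05 can be used for it without the overall error exceeding 0.05. The fixed rule leaves that part of the accepted error unspent.

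At stake is the second claim. The trial asks two questions against one placebo arm, and 8.4 itself expects any difference between the two active regimens to be smaller than the design effect. Two active arms of similar or moderately unequal benefit is therefore a case the sponsor has in mind. In that case the fixed rule will sometimes leave a second effective arm unconfirmed although the stated error limit would have allowed the claim.

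**Working it through.** **Inputs (Protocol 8.4).** Placebo mean 0.360 on the log(Y+1) scale, which is exp(0.36) − 1 = 0.433 nmol/L; residual SD 0.167; 50% increase; 26 complete per group; 1:1:1 allocation; one-sided 0.025 per test. Because the placebo arm is shared and the groups are equal, the two test statistics correlate at 0.5.

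**Reproducing the stated power.**
- Effect: log(1 + 1.5 × 0.4333) − 0.36 = 0.1408.
- Standard error: 0.167 × √(2/26) = 0.0463.
- θ = 0.1408 / 0.0463 = 3.04.
- Power: Φ(3.04 − 1.96) = 86.0%; with t critical values (72 df) 85.1%. The protocol's 85% is confirmed.

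**The two rules, single final analysis.**
- Fixed: reject both if both Z > 1.960.
- Holm: reject both if the larger Z > 1.960 and the smaller Z > 1.645.

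Bivariate normal, correlation 0.5, 26 per group:

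| Quantity | Fixed 0.025/0.025 | Holm |
|---|---|---|
| Both arms +50%: at least one rejected | 94.8% | 94.8% |
| Both arms +50%: both rejected | 77.2% | 85.5% |
| Both arms +50%: power for a given arm | 86.0% | 90.1% |
| One arm +50%, other +28%: power for the other | 42% | 53% |
| Error, both nulls true | 0.045 | 0.045 |
| Error, one null true, other arm +50% | 0.025 | 0.0497 |

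The +28% row is an illustrative scenario and does not come from the protocol. Its θ is [log(1 + 1.28 × 0.4333) − 0.36] / 0.0463 = 1.75.

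**Sensitivity of the probability of rejecting both (both arms +50%).** With t critical values, 76.0% to 84.7%. With θ = 3.00 as in 8.6, 75.9% to 84.5%. With 28 complete per group, 80.8% to 88.1%.

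**Equivalent sample size.** Under the fixed rule, 31 complete per group gives θ = 0.1408 / (0.167 × √(2/31)) = 3.32 and about 85% for both. That is 3 × (31 − 26) = 15 more complete participants than the planned 78.

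**With an interim look.** The 8.6 spending function at t* = 0.5 gives:
- α = 0.025: 2 − 2Φ(2.241/√0.5) = 0.0015, boundary Z = 2.96.
- α = 0.05: 2 − 2Φ(1.960/√0.5) = 0.0056, boundary Z = 2.54.

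Assume one look at t* = 0.5, placebo closed on any crossing, no futility closure, and both arms at +50%. About a third of simulated trials then stop at that look. The chance of rejecting both is about 56% under the fixed rule. It is about 71% under Holm if the remaining hypothesis is tested against 2.54 at the same look, before placebo closes.

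**The case against.** The strongest reply is that nothing here is wrong. Two one-sided 0.025 tests give an overall error between 0.045 (shared placebo) and 0.05 (the bound), so the sentence in 8.4 is accurate and 8.6 agrees with it. Holding every claim to one-sided 0.025 is a defensible evidential standard, and the extra power is not free: if only one arm works, the chance of falsely claiming the other doubles. All of this stands. It makes the point an efficiency proposal that the sponsor may decline for a stated reason.

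Three stronger readings are tempting, and the protocol does not support them.

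- *That the 0.05 goes unused.* About 0.045 of it is spent when both nulls are true. The unspent part appears when one arm is truly effective.
- *That the choice between regimens suffers most, because 8.4 places it after a double rejection.* Holm adds only cases where one arm has Z above 1.960 and the other lies between 1.645 and 1.960. With equal groups and one model, the arm with the larger Z also has the larger adjusted mean, apart from small differences in standard error. It is the arm the selection rule would choose, and it is the only arm rejected under the fixed rule. The regimen taken forward is therefore the same. Under 8.7, selection can also proceed after a single boundary crossing. Only the second claim against placebo changes.
- *That 77% and 85% describe the trial as it will run.* They hold for one final analysis. With efficacy stopping and placebo closure both figures are lower, although a gain remains.

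**Conclusion.** The point holds as an inexpensive improvement. Within the overall error the protocol already accepts, Holm never rejects less than the fixed rule. When both arms have the design effect, it adds about 8 percentage points to the chance of confirming both at a single final analysis, and about 15 points (56% to 71%) with one look at half the information.

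The family-wise limit itself does not depend on the correlation. The power figures assume the protocol's SD and placebo mean, 26 complete participants per group, correlation 0.5 and, except where stated, the full 50% effect in both arms. The interim figures further assume one look at t* = 0.5, no futility closure, and testing of the second hypothesis before placebo closes. If placebo closes first, little or no gain remains in trials that stop early.

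**What to change.** In 8.4, state that both hypotheses are tested at one-sided 0.025 and that, if one is rejected, the other is tested at one-sided 0.05 (Holm).

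In 8.6 and 8.7, pre-specify the Lan-DeMets boundary with α = 0.05 for the remaining hypothesis. State that it is applied at the same look at which the first boundary is crossed, before the placebo arm is closed. Report which hypothesis was rejected first and at what level each was tested.

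Make the change before any unblinded comparative result is seen.

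The cost is a short amendment and one extra boundary calculation; participants, visits and the stated overall 0.05 stay as they are. The downside should be disclosed: a second claim may rest on a one-sided p between 0.025 and 0.05, and with one inactive arm the chance of falsely claiming it rises from 0.025 to about 0.05. If the sponsor prefers 0.025 for every claim, one sentence giving that reason would settle the matter.
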